7.2 Clinical Laboratory Assessments

7.2.1 Hematology

Blood will be obtained and sent to the clinical site hematology lab for complete blood count (hemoglobin, hematocrit, red blood cell count, white blood cell count, white blood cell differential, and platelet count) and C-reactive protein (CRP) as per time and events table (section 8.0).

7.2.2 Blood Chemistry Profile

Blood will be obtained and sent to the clinical site chemistry lab for determination of serum creatinine, total bilirubin, albumin, lactate dehydrogenase, and the following as deemed necessary per SOC: sodium, potassium, chloride, bicarbonate, glucose, blood urea nitrogen, aspartate aminotransferase, alanine aminotransferase, and alkaline phosphatase.

7.2.3 HIV viral load and CD4 count

Will be assessed for all HIV-infected subjects.

7.2.4 Hepatitis B serologies

Hepatitis B surface antigen will be assessed for all HIV negative subjects at baseline.

7.2.5 Pregnancy Test

A urine pregnancy test will be obtained from female subjects who are of childbearing age prior to their participation in the study.

7.3 Quality of life assessment

Symptoms and quality of life will be assessed by the MCD symptom score and PROMIS-Preference, as adapted for UNC Project Malawi previously.

7.4 Correlative Studies

We plan to conduct correlative studies, including viral and host genomics (of the tumor sample only), cytokine studies, and KSHV viral load. Host genomic studies will be completed in the Vironomic core at UNC Chapel Hill from formalin-fixed paraffin-embedded biopsy specimens and will focus on both the malignant plasmablasts as well as the surrounding tumor microenvironment, but no specific germline mutation testing will be completed. This biopsy is standard of care and is required for diagnosis and entry into this study. If insufficient tissue is available, subjects can still participate in the clinical trial. Viral genomic studies will be conducted from the same biopsy specimen or from plasma samples taken for cytokine studies as outlined below.

Cytokine studies will require blood draws of 10 mL (2 heparin tubes separated into plasma and PBMCs) and 1 tube (5 mL) with citrate at baseline, mid-treatment (day 15), end-of-treatment (day 29), first follow-up (12 weeks) after start of treatment, and at all long term follow up visits. Samples will be stored at -80 °C.

8.0 EVALUATIONS AND ASSESSMENTS

8.1 Time and Events Table (Table 7)

Table 7: Time and Events Table.	Initial Visit or Relapse ¹	Treatment days 1, 8, 15, and 22 ²	End-of-treatment (Week 5)	Follow-up (12 weeks)	Long term follow up ⁴
Informed consent	Initial visit only				
History & physical exam ⁵	X	X	X	X	X
Concomitant medications ⁶	X	X	X		
ECOG performance status ⁷	X	X	X		
Toxicity evaluation ⁸	X	X	X	X	X ⁸
Tumor biopsy ⁹	X				
Survival ¹⁰		X	X	X	X
Treatments ¹¹		X			
Lymph node measurements	X	Day 15 only	X	X	X
MCD-SS and Quality of life assessment ¹²	X	Day 15 only	X	X	X ¹²
Chest X-ray and abdominal ultrasound	X		X ¹³		
Hematology & blood chemistries ¹⁴	X ¹⁵	X ¹⁶	X	CBC only	CBC only
Correlative blood samples ¹⁷	X	Day 15 only	X	X	X ¹⁹
Lactate dehydrogenase	X	Day 15 only	X		

Viral and host genotyping	X	
Urine pregnancy test	X ¹⁸	
Hepatitis B (for HIV-negative patients)	X	
CD4 and HIV RNA (if HIV positive)	X	X ¹⁹

¹ Screening assessments must be completed within 21 days prior to study enrollment.

² A window of +/- 7 days will apply to all study visits; however, lymph node measurements must take place prior to that cycle's treatment.

³ End-of-treatment visit should occur 7-14 days from final dose of chemotherapy. A subject who is being withdrawn for disease progression or for other reasons (e.g. unacceptable toxicity, etc.) should complete an end of treatment visit.

⁴ Long term follow-up will occur every 3 months until 24 months after the start of treatment unless otherwise noted.

⁵ After the initial visit (comprehensive history and physical exam) subsequent visits will address a focused history and physical exam.

⁶ All concomitant medications will be recorded.

⁷ See Appendix E. ECOG Performance Status

⁸ per NCI CTCAEv5.0 for notation of baseline toxicity. Assess from initial visit through first follow-up visit (12 weeks) and again at the final follow up visit (24 months).

⁹ Archival and/or fresh sample.

¹⁰ Survival will be assessed at each visit through out the duration of treatment, follow up, and long term follow up.

¹¹ Subjects with low risk disease will receive rituximab at 375 mg/m² weekly for 4 weeks. High risk subjects will receive rituximab at 375 mg/m² and etoposide at 100 mg/m² weekly for 4 weeks.

¹² Quality of life assessment includes PROMIS Global 10, MCD-SS and QoL will be assessed through follow up, and at 24 months during long term follow up. QoL will also be assessed at the time of any relapse.

¹³ Omitted if no baseline abnormalities on chest x-ray and abdominal ultrasound.

¹⁴ Hematology assessments include hemoglobin, white blood cell count, white blood cell differential, and platelet count. Blood chemistry assessments include serum creatinine, total bilirubin, albumin, and the following as deemed necessary per SOC: sodium, potassium, chloride, bicarbonate, glucose, blood urea nitrogen, aspartate aminotransferase, alanine aminotransferase, and alkaline phosphatase. See the T&E table for when lactate dehydrogenase is measured.

¹⁵ If a patient has been tested for hemoglobin within 1 month of enrollment and received a blood transfusion due to low hemoglobin, then the original test will dictate treatment group (high vs low risk).

¹⁶ Hemoglobin and platelet count will be assessed per SOC during treatment.

¹⁷ Blood sample for correlates will include assessments of C-reactive protein, KSHV viral load from plasma and PBMCs, and cytokine levels (IL-6, IL-10, IL-2, TNF α , INF γ). KSHC genotyping will occur on the first draw only. Blood draws will be two 10 mL tubes (2 heparin tubes separated into plasma and PBMCs) and 1 tube (5 mL) with citrate. Correlative blood samples collected during long term follow up will be stored and analyzed

¹⁸ In women under 60 years of age, required within 3 days of start of treatment.

¹⁹ At 12 and 24 month long term follow up visits.

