5.2 Treatment Dosage and Administration

Treatment will be administered on an outpatient basis in the Kamuzu Central Hospital cancer clinic, as per **Table 1**, where chemotherapy is currently administered.

Table 1: REGIMENT DESCRIPTION			
Agent	Premedications	Dose and Route	Schedule
Rituximab	Premedicate with diphenhydramine 50 mg IV and acetaminophen 650 mg PO 1 hour prior to rituximab.	
375 mg/m² rounded to the nearest 100 mg to avoid vial waste (dilute in normal saline or 5% dextrose to a final concentration of 1-4 mg/ml).
 
Administer via slow IV infusion, starting at 50mg/hr and increasing by 50mg/hr every 30 minutes to a maximum infusion rate of 400mg/hr.
 
CAUTION: DO NOT ADMINISTER AS AN INTRAVENOUS PUSH OR BOLUS. IV pumps such as the IMED 960 may be used with the rituximab infusion.
 
DO NOT INFUSE CONCOMITANTLY with another IV solution or IV medications. Prime the line with the rituximab solution such that approximately 30 mL are delivered. This will saturate the filter and tubing.
	Days 1, 8, 15, 22
Etoposide	n/a	
100 mg/m² (dilute to final concentration 0.2-0.4 mg/mL in either normal saline or 5% dextrose)
 
IV over 1 hour after completion of rituximab
	Days 1, 8, 15, 22

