5.3 Toxities and Dosing Delays/Dose Modifications

Any patient who receives treatment on this protocol will be evaluable for toxicity. Each patient will be assessed periodically for the development of any toxicity according to the Time and Events table (Section 8.1). Toxicity will be assessed according to the National Cancer Institute (NCI) CTCAE, v5.0. Dose adjustments should be made according to the system showing the greatest degree of toxicity. See **Tables 2-4** below for recommended dose delays/dose modifications.

Assigning cause of death is often difficult in Malawi because diagnostic capabilities are limited and deaths frequently occur outside of health facilities. To address this challenge, two senior non-study clinicians will be enlisted to review all study data for deceased patients and assign cause of death as either likely treatment-related, MCD-related, related to another cause, or unable to determine. In the event of discordant conclusions, a third senior clinician will serve as a tiebreaker.

Table 2: Hematological toxicity dose reductions		
ANC	Platelets	Action
≥ 0.5 x 10 ³ /µL	≥ 50 x 10 ³ /µL	None.

$< 0.5 \times 10^3/\mu\text{L}$	$< 50 \times 10^3/\mu\text{L}$	
FIRST EPISODE: Hold current etoposide dose until ANC $\geq 0.5 \times 10^3/\mu\text{L}$ and platelets $\geq 50 \times 10^3/\mu\text{L}$. Restart next treatment at 75 mg/m^2. Do NOT hold or reduce rituximab dose.
 
SECOND EPISODE: Hold current etoposide dose until ANC $\geq 0.5 \times 10^3/\mu\text{L}$ and platelets $\geq 50 \times 10^3/\mu\text{L}$. Restart next treatment at 50 mg/m^2. Do NOT hold or reduce rituximab dose.
 
Goal is to replace doses and complete full course of four doses of both etoposide and rituximab.

---------------------------------	--------------------------------	--

Table 3: Non-hematological toxicity dose reductions for rituximab	
NCI CTC Grade	
0-2	No change from original dose.
3-4	Wait until resolved to \leq Grade 2, no dose reduction.
Second episode of Grade 3 or 4 toxicity	Hold until resolved to \leq Grade 2, no dose reduction.
Third episode of Grade 3 or 4 toxicity	Remove subject from trial

Table 4: Hepatic and renal dysfunction dose adjustment for etoposide	
Event	Action
Renal dysfunction	
Cr clearance $>50 \text{ ml/min}$	None
Cr clearance 15-50 ml/min	Decrease dose to 75 mg/m^2
Cr clearance $<15 \text{ ml/min}$	Decrease dose to 50 mg/m^2
Hepatic dysfunction	
Bilirubin $<1.5 \text{ mg/dL}$	None

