6.2.1 Adverse events associated with etoposide

The following data on adverse reactions are based on both oral and IV administration of etoposide as a single agent, using several different dose schedules for treatment of a wide variety of malignancies.

Hematologic Toxicity: Myelosuppression is dose related and dose limiting with granulocyte nadirs occurring 7 to 14 days after drug administration and platelet nadirs occurring 9 to 16 days after drug administration. Bone marrow recovery is usually complete by day 20, and no cumulative toxicity has been reported. The occurrence of acute leukemia with or without a preleukemic phase has been reported rarely in patients treated with etoposide in association with other antineoplastic agents.

Gastrointestinal Toxicity: Nausea and vomiting are the major gastrointestinal toxicities. The severity of such nausea and vomiting is generally mild to moderate with treatment discontinuation required in 1% of patients. Nausea and vomiting can usually be controlled with standard antiemetic therapy. Gastrointestinal toxicities are slightly more frequent after oral administration than after IV infusion.

Hypotension: Transient hypotension following rapid IV administration has been reported in 1% to 2% of patients. It has not been associated with cardiac toxicity or electrocardiographic changes. No delayed hypotension has been noted. To prevent this rare occurrence, it is recommended that etoposide be administered by slow IV infusion over a 30- to 60-minute period. If hypotension occurs, it usually responds to cessation of the infusion and administration of fluids or other supportive therapy

as appropriate. When restarting the infusion, a slower administration rate should be used.

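### The +/- 7 day visit window covers the weekly dosing visits and no minimum gap between etoposide doses is stated, so doses only days apart count as in-window

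*Combined protocol and SAP*

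**What the plan says.** Section 5.2, Table 1, schedules rituximab and, for high-risk patients, etoposide 100 mg/m² on days 1, 8, 15 and 22. Etoposide is given "IV over 1 hour after completion of rituximab". Sections 1.1, 5.1, 5.7, 10.1 and 10.4.1 also describe the regimen as weekly.

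In Section 8.1, footnote 2 is marked on the column headed "Treatment days 1, 8, 15, and 22" and reads: "A window of +/- 7 days will apply to all study visits". Its only added condition is that lymph nodes are measured before that cycle's treatment. It says nothing about spacing between doses.

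Section 5.3, Table 2, holds the current etoposide dose until neutrophils and platelets recover to stated thresholds. For a first episode it then says "Restart next treatment at 75" mg/m², and for rituximab "Do NOT hold or reduce rituximab dose". It ends: "Goal is to replace doses and complete full course of four doses of both etoposide and rituximab". Release depends on counts alone; no number of days is given.

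Section 6.2.1 reports "granulocyte nadirs occurring 7 to 14 days after drug administration" and "platelet nadirs occurring 9 to 16 days after drug administration". Section 5.4.1 says that G-CSF will not be routinely available.

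**The concern.** A tolerance as wide as the dosing interval places no limit on how close two doses may be. Table 2 then leaves a practical question open: is a held etoposide dose given as soon as counts recover, or at the next rituximab visit? Rituximab keeps its weekly schedule, and etoposide is tied to rituximab days. If a held dose is given between visits, the next paired visit can therefore follow within a few days.

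What is at stake is how much the hold rule can show. A count taken a few days after a dose comes before the time when the protocol expects that dose to have its greatest effect. It may look acceptable when the next dose is due, in a high-risk patient who has already had one hold for low counts and for whom G-CSF is not routinely available.

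**Working it through.** The plan gives no figure for dose spacing, so there is none to reproduce. The check is calendar arithmetic on stated inputs: nominal days 1, 8, 15 and 22 (Table 1); window w = 7 days (footnote 2); granulocyte nadir 7-14 days and platelet nadir 9-16 days after a dose (Section 6.2.1). Dose 1 is fixed at day 1.

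**Step 1: windows.** Allowed days are nominal day - w to nominal day + w. With w = 7, dose 2 may fall on days 1-15, dose 3 on days 8-22 and dose 4 on days 15-29. The smallest in-window gap between later doses is 7 - 2w, and from dose 1 to dose 2 it is 7 - w.

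| w (days) | Smallest gap, dose 1 to 2 | Smallest gap, later doses |
|---|---|---|
| 7 (current) | 0 | -7 (windows overlap) |
| 3 | 4 | 1 |
| 2 | 5 | 3 |
| 1 | 6 | 5 |

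The current rule sets no positive minimum. Narrowing a symmetric window to 2 or 3 days would still allow later doses 1 to 3 days apart. As an outer limit and not a forecast, doses on days 1, 2, 8 and 15 are all in-window: a span of 14 days instead of 21.

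**Step 2: the two readings of Table 2**, for etoposide held on day 8 with rituximab continuing on days 8, 15 and 22.

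- *Given on recovery*, say day 12: etoposide on days 1, 12, 15, 22, with gaps of 11, 3 and 7 days. All are in-window.
- *Given at the next rituximab visit*: etoposide on days 1, 15, 22, 29, with gaps of 14, 7 and 7 days. All are in-window.

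**Step 3: what the count check can show.** For a gap of g days, a count taken at the next dose falls 7 - g days before the granulocyte nadir range opens and 9 - g days before the platelet range opens. This assumes that the stated ranges apply after each weekly dose.

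| Gap g (days) | Days before granulocyte range | Days before platelet range |
|---|---|---|
| 3 | 4 | 6 |
| 6 | 1 | 3 |
| 7 (planned) | 0 | 2 |

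In the day-12 example the granulocyte range is days 19-26, so a day-15 count is 4 days early. Planned weekly dosing already checks at the earliest edge of that range and before the platelet range. Footnote 2 does not create that limit but lets it widen.

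**Step 4: does a limit on early visits suffice?** Allowing at most 1 day early gives earliest days 7, 14 and 21. Days 1, 12, 15, 22 still pass. A 6-day minimum gap rejects them (3 < 6) and accepts days 1, 15, 22, 29.

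**Step 5: end-of-treatment visit.** Footnote 3 places it 7-14 days after the final dose. With a last dose on day 29 that is days 36-43. Section 7.4 puts the visit at day 29, and +/- 7 gives days 22-36. Only day 36 satisfies both.

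**The case against.** The strongest reply is that the interval is not in doubt. The regimen is called weekly throughout, Section 11.4 requires the study to be run as described, and a visit tolerance in an assessment table does not rewrite Section 5.2. The restart wording in Table 2, read with Table 1's pairing of the two drugs, can naturally mean the next rituximab visit, and Table 7 has no day-12 visit. This stands in part: the 3-day gap is one possible reading, not an instruction. But footnote 2 is the rule that defines acceptable departure from the nominal days, and the hold-until-recovery and replace-doses wording supports the other reading.

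The example also needs a patient held on day 8 to recover by day 12, inside the day-1 dose's own nadir range (days 8-15). That is possible, but the documents do not say how often it would happen.

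A reader might infer that the window permits overdosing. The documents do not support that. In the example, 2 x 75 = 150 mg/m² falls within days 12-15, against at most 100 mg/m² in any 7 planned days. Over days 8-15, however, the comparison reverses: 150 against 200 mg/m² planned. Cumulative dose is lower by day 15 (100 + 75 + 75 = 250 against 300) and over the course (325 against 400).

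A reader might also infer that short spacing is dangerous in itself. Section 1.4 describes a Kaposi sarcoma trial of daily oral etoposide on days 1-7 of 14-day cycles with no study-related deaths, and Section 6.2.1 reports no cumulative marrow toxicity. Route and disease differ, but nothing in the protocol shows that close spacing alone causes harm.

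**Conclusion.** The point holds as a modest patient-safety issue. On its text, footnote 2 sets no minimum on the spacing of weekly doses, no other section supplies one, and Table 2 is unclear about when a held etoposide dose is given. On one of its two readings, a dose 3 days after the last is in-window, with a count check 4 days before the granulocyte nadir range opens.

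The issue concerns high-risk patients, mainly those with a count-triggered hold. It rests on the protocol's own nadir ranges applying after each weekly dose and on the first reading of Table 2. Its frequency and the size of any harm are not quantified and cannot be from these documents. A reader might infer that the trial's main result is compromised. It is not: the primary endpoint definition (non-hematologic Grade 3 or higher events and treatment-related mortality), the sample size and the power do not depend on dose spacing. The change should be made because it is specific and cheap.

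**What to change.** Keep +/- 7 days for follow-up visits. For dosing visits, allow at most about 1 day early, keep late tolerance for toxicity holds, and require at least 6 days between etoposide doses. The minimum gap is essential, because the early limit alone does not exclude the 3-day gap. The exact number of days is for the sponsor to settle.

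In Table 2, state that a held etoposide dose is given at the next rituximab visit once counts have recovered, that rituximab continues weekly, and that the missed dose is added at the end (for example days 1, 15, 22, 29). A dose held on day 22 has no later rituximab visit, so the text should name the next weekly slot for that case. State also that the end-of-treatment visit follows footnote 3, 7-14 days after the final dose, when this conflicts with the nominal day.

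The cost is a revised footnote and a few lines in Table 2, a few more recorded deviations, and an occasional etoposide-only visit (one in the example, on day 29). For those patients the end-of-treatment visit comes about a week later: days 36-43, against a nominal day 29 +/- 7. Their end-of-treatment assessments move with it.

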1.0 BACKGROUND AND RATIONALE

1.1 Study Synopsis

In sub-Saharan Africa (SSA), Kaposi sarcoma herpesvirus (KSHV)-related cancers account for 10-35% of malignancies¹⁻³ and >10% of cancer-related deaths.³ Multicentric Castleman disease (MCD) is a life-threatening lymphoproliferative disorder characterized by systemic inflammation and lymphadenopathy. MCD is strongly associated with KSHV and human immunodeficiency virus (HIV). KSHV seroprevalence in SSA is >40%,^{4,5} the highest of any region in the world; likewise, the prevalence of HIV is high.⁶ Substantial knowledge gaps remain regarding treatment for MCD, including outcomes, safety, and cost-effectiveness, particularly in SSA.

MCD can be controlled with chemotherapy. When chemotherapy is discontinued, however, rapid relapses or development of non-Hodgkin lymphoma (NHL) occur with high mortality.^{7,8} Long-term remission is achieved in most patients with rituximab, an anti-CD20 monoclonal antibody, as described in small clinical trials in high-income countries (HIC).⁹⁻¹¹ However, rituximab has not been evaluated for MCD in SSA, nor are there published safety data for rituximab from the region.

In this study, we aim to determine the safety and efficacy of first-line, risk-stratified rituximab-based MCD treatment in Malawi in a single-arm, phase II clinical trial. We will enroll 27 subjects with newly diagnosed or previously treated MCD (who have not previously received rituximab) requiring treatment (B symptoms or hemoglobin <10 g/dL).¹² Subjects will be treated with four weekly doses of rituximab. High-risk subjects (defined as patients with Eastern Cooperative Oncology Group (ECOG) performance status >2 or hemoglobin <8 g/dL)^{9,10,13-16} will also receive etoposide chemotherapy.^{9,11} Subjects will be followed for one year for toxicity and two years for survival. The primary outcome will be safety, defined as the frequency of \geq Grade 3 treatment-related Common Terminology Criteria for Adverse Events (AEs). Secondary outcomes will be event-free survival (death, progression, or development of NHL) and 1- and 2-year overall survival (OS). We also aim to compare the cost-effectiveness of first-line rituximab treatment for MCD in Malawi to chemotherapy (using our historical controls).

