6.1.6 Adverse Events Associated with Investigational Drug

Human Toxicology: Single doses of up to 2275 mg/m² and weekly x 4 doses of 375 mg/m² have been administered without dose limiting toxicity. AEs are most common during the initial antibody infusion and usually consist of Grade 1 or 2 fever (73%), asthenia (16%), chills (38%), nausea (19%), vomiting (11%), rash (14%) and tumor site pain (3%). Grade 1 or 2 hypotension (8%) may be treated

with IV fluids. Hematologic toxicity is usually mild and reversible. Transient decreases in the WBC or platelet count have been observed - especially in patients with high levels of circulating tumor cells or bone marrow involvement. Two patients have had late-onset Grade 4 neutropenia at four and ten months that was attributed to an unknown cause, was transient, and resolved. Infections (Grade 1 and 2) have not been related to dose level. Symptoms are generally associated with the initial antibody infusions and diminish in frequency with each successive infusion. A report in the literature described an increase in fatal infection in HIV-related lymphoma patients when rituximab was used in combination with CHOP chemotherapy as compared to CHOP alone.

Severe Infusion and Hypersensitivity Reactions: Rituximab has caused severe infusion reactions. In some cases, these reactions were fatal. An infusion-related symptom complex consisting of fever and chills/rigors has occurred in many patients during the first rituximab infusion. Signs and symptoms of severe infusion reactions may include urticaria, hypotension, angioedema, hypoxia, or bronchospasm. The most severe manifestations and sequelae include pulmonary infiltrates, acute respiratory distress syndrome, myocardial infarction, ventricular fibrillation, cardiogenic shock, and anaphylactic and anaphylactoid events. These reactions generally occurred within 30 minutes to 2 hours of beginning the first infusion, and resolved with slowing or interruption of the rituximab infusion and with supportive care (including, but not limited to IV saline, diphenhydramine, and acetaminophen).

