Tumor Lysis Syndrome: Rituximab rapidly decreases benign and malignant CD20 positive cells. Tumor lysis syndrome has been reported to occur within 12 to 24 hours after the first rituximab infusion in patients with high numbers of circulating malignant lymphocytes. Patients with high tumor burden (bulky lesions) may also be at risk. Patients at risk for developing tumor lysis syndrome should be followed closely and appropriate laboratory monitoring performed.

Hepatitis B Reactivation with Related Fulminant Hepatitis and Other Viral Infections: Hepatitis B virus (HBV) reactivation with fulminant hepatitis, hepatic failure, and death has been reported in some patients with hematologic malignancies treated with rituximab. The majority of patients received rituximab in combination with chemotherapy. The median time to diagnosis of hepatitis was approximately four months after the initiation of rituximab and approximately one month after the last dose. Persons at high risk of HBV infection should be screened before initiation of rituximab. Carriers of hepatitis B should be closely monitored for clinical and laboratory signs of active HBV infection and for signs of hepatitis during and for up to several months following rituximab therapy. In patients who develop viral hepatitis, rituximab and any concomitant chemotherapy should be discontinued and appropriate treatment, including antiviral therapy, initiated. There are insufficient data regarding the safety of resuming rituximab therapy in patients who develop hepatitis subsequent to HBV reactivation. The following additional serious viral infections, either new, reactivated or exacerbated, have been identified

in clinical studies or postmarketing reports. The majority of patients received rituximab in combination with chemotherapy or as part of a hematopoietic stem cell transplant. These viral infections included John Cunningham virus, which is associated with progressive multifocal leukoencephalopathy, cytomegalovirus, herpes simplex virus, parvovirus B19, varicella zoster virus, West Nile virus, and hepatitis C. In some cases, the viral infections occurred up to one year following discontinuation of rituximab and have resulted in death.

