7.1.3 Medical History

Relevant medical history, including history of current disease, other pertinent respiratory history (e.g., tobacco use), and information regarding underlying diseases will be recorded at screening and a focused medical history of symptoms/toxicity will be performed thereafter.

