7.1.5 Adverse Events

Events should be assessed per NCI-CTCAE criteria v5.0. Information regarding occurrence of AEs will be captured throughout the study. Duration (start and stop dates), severity/grade, outcome, treatment, and relation to study drug will be recorded in the eCRF. PRO-CTCAE has recently been translated and validated in Malawi and will be used to capture patient reported adverse events.

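### The protocol states one year of toxicity follow-up, but no schedule delivers it: evaluation pauses from week 12 to month 24, and AE/SAE recording ends 30 days after treatment

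*Combined protocol and SAP*

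**What the plan says.** The protocol gives several different periods for toxicity follow-up.

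- Section 1.1: "Subjects will be followed for one year for toxicity and two years for survival".
- Section 7.1.5: "Information regarding occurrence of AEs will be captured throughout the study".
- Section 8.1, Table 7, footnote 8, on toxicity evaluation: "Assess from initial visit through first follow-up visit (12 weeks) and again at the final follow up visit (24 months").
- Sections 9.2 and 9.3.1: documentation of non-serious events and recording of SAEs both run from day 1 to 30 days after treatment is discontinued.
- Section 10.5.3: the description of all AEs stops 30 days after the final dose.
- Sections 3.1 and 3.2.6: the primary and additional safety endpoints run to 12 weeks from the start of therapy.

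On visits, footnote 4 of Table 7 says: "Long term follow-up will occur every 3 months until 24 months after the start of treatment unless otherwise noted". The long-term column has history and examination, survival, lymph node measurements and a CBC. Chemistries and concomitant medications are not marked after the end-of-treatment visit.

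On late toxicity, section 6.1.6 reports: "Two patients have had late-onset Grade 4 neutropenia at four and ten months". It also describes viral infections, in some cases up to one year after rituximab was stopped. For hepatitis B it says: "The median time to diagnosis of hepatitis was approximately four months after the initiation of rituximab". The same sentence adds a second timing, about one month after the last dose. The section also speaks of following carriers for clinical and laboratory signs for several months after therapy.

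**The concern.** Safety is the primary objective, and the stated rationale is that rituximab safety data from the region are lacking in a setting with a high infection burden. One year of toxicity follow-up is a reasonable commitment in that light, but sites will work from Table 7 and section 9. Read literally, these tell them not to perform a toxicity evaluation between week 12 and month 24, and not to record AEs or SAEs beyond 30 days after treatment.

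A clinician who sees a serious infection at month 6 may well note it in the chart. Whether it becomes trial data depends on which section the site follows. Late toxicity would then be recorded unevenly, and a reader could not tell an absence of events from an absence of recording. A single evaluation at month 24 is a weak substitute, because it reaches only patients who are alive and in contact and asks them to recall some 21 months.

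**Working it through.** **The plan's own design figure.** Section 10.2 gives n = 24, at most 6 events, a null rate of 40%, an expected rate of 20%, and 27 enrolled. Exact binomial: P(X ≤ 6 | 24, 0.40) = 0.096, below 0.1. P(X ≤ 6 | 24, 0.20) = 0.811, against 80% stated. 24/0.9 = 26.7, rounded up to 27. All reproduce, and the present point does not touch them.

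**Inputs for the schedule.** One month = 365.25/12 = 30.44 days. The last scheduled dose is on day 22 (section 5.2). Long-term visits are taken as months 6, 9, 12, 15, 18, 21 and 24, which assumes that the 12-week visit serves as month 3.

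**Coverage of the stated year**

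- 12 weeks = 84/30.44 = 2.76 months.
- Week 12 to month 12: 12 − 2.76 = 9.24 months with no scheduled toxicity evaluation. That is 9.24/12 = 77% of the stated year.
- Recording under 9.2 and 9.3.1: day 22 + 30 = day 52, or (21 + 30)/7 = 7.3 weeks from the start. This is shorter than the 12-week safety endpoints themselves.
- Week 12 to month 24: 24 − 2.76 = 21.2 months (about 646 days). Six of the seven long-term visits have no toxicity evaluation, and three of those six (months 6, 9 and 12) lie within the stated year.

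**Where the cited late events fall**

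| Event in section 6.1.6 | Time from start | Position |
|---|---|---|
| Late neutropenia, case 1 | month 4 | after week 12, before the 6-month visit |
| Late neutropenia, case 2 | month 10 | between the 9- and 12-month visits |
| Viral infections, upper limit | (21 + 365.25)/30.44 = month 12.7 | range reaches the 6-, 9- and 12-month visits |
| Hepatitis B median, from initiation | 4 × 30.44 = day 122 | after week 12, before month 6 |
| Hepatitis B median, from last dose | 22 + 30.4 = day 52 | week 7, inside the 12-week window |

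The text gives no anchor for the two neutropenia times; they are read here as months from the start of treatment.

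Both neutropenias, and viral infections up to the one-year limit, can fall after week 12, when sections 9.2, 9.3.1 and 10.5.3 have already closed. The hepatitis B timing settles nothing, because its two anchors give different answers for a 22-day course.

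**The case against.** The case for leaving the schedule alone has substance.

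- Both safety endpoints are defined through 12 weeks, and footnote 8 fits that scope.
- The long-term visits are not empty. Footnote 5 says "subsequent visits will address a focused history and physical exam", and section 7.1.3 says "a focused medical history of symptoms/toxicity will be performed thereafter". Section 10.2 also speaks of grading toxicity at each clinic visit.
- The CBC includes a differential, so neutropenia present at a visit would be measured.
- Survival is checked at every visit, and section 5.3 has non-study clinicians assign the cause of each death. Late deaths are therefore recorded and adjudicated.
- The first column of Table 7 also covers relapse and includes a toxicity evaluation.
- The eligibility criteria on tenofovir or lamivudine bear on the hepatitis B risk.

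These points limit the size of the problem but do not remove it. A focused history or a blood count does not create a required AE record when section 9 has closed the recording window and footnote 8 omits the visit. The cited neutropenias were transient, so a three-monthly count could miss them. Sections 7.1.5 and 10.2 favour continued capture, but footnote 8 and section 9 contradict them.

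Four stronger readings are tempting and not supported:

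- *More than half of hepatitis B reactivations would fall in the gap.* This holds only on the initiation anchor. On the last-dose anchor the median is at week 7.
- *Some 89% of follow-up is uncovered* (21.2/24). This counts a second year for which the synopsis states no toxicity follow-up.
- *The trial would be nearly silent on delayed toxicity.* Deaths, blood counts and examinations continue to month 24.
- *The cited toxicities fall at the 15- to 21-month visits.* No timing in section 6.1.6 goes beyond about month 12.7.

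**Conclusion.** The point holds as an internal contradiction with a practical consequence. Toxicity follow-up is variously one year, the whole study, 12 weeks plus month 24, and 30 days after treatment. No schedule delivers the stated year: about 9.2 of its 12 months lack a toxicity evaluation, and the section 9 recording windows close at about day 52. Events of kinds that the protocol itself cites can fall in that interval and have no clear recording requirement.

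This should be corrected, but it does not threaten the primary result. The 12-week endpoint, the exact test and the sample size are unchanged. The conclusion assumes on-schedule dosing and the 12-week visit serving as month 3. It does not depend on the hepatitis B timing.

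Separately, section 6.1.6 describes laboratory follow-up of hepatitis B carriers for several months, while Table 7 schedules only a CBC after end of treatment. These passages must be reconciled; which of them is clinically right is not a matter for this review.

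**What to change.** Reconcile the passages to the stated one year:

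1. In Table 7 and footnote 8, mark toxicity evaluation (Grade ≥3 AEs, infections and SAEs) at the existing 6-, 9- and 12-month visits, and keep month 24.
2. Extend the recording and reporting windows in sections 9.2, 9.3.1 and 10.5.3 to match. Without this step, the new marks in Table 7 would conflict with section 9.
3. Align sections 1.1 and 7.1.5 with the same wording.
4. Report late toxicity from week 12 through one year descriptively, and state that it does not enter the 12-week primary endpoint or the section 10.2 test.
5. Reconcile the hepatitis B monitoring text in section 6.1.6 with the CBC-only entries in Table 7.

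Shortening the synopsis and section 7.1.5 instead would remove the contradiction but leave late events without a recording rule.

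The cost is a protocol and eCRF amendment and modest extra data entry at three visits that already take place. The 24-hour SAE notification in section 9.3.2 would then also run to one year, and the amendment should say so. No visits are added.
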